### **6.7.2. Bleeding Events**

All information obtained on bleeding events will be displayed by treatment group.

The number and percentage of patients with bleeding events will be tabulated by SOC and PT with a breakdown by treatment. A patient with multiple bleeding events is only counted once towards the percentage of patients with bleeding events.

Gastrointestinal bleeding events may include AEs with MedDRA terms associated with gastrointestinal hemorrhage or adjudicated as being located in the Upper GI or Lower GI, by the CEC.

The proportion of patients having received transfusions, as well as the number of blood units transfused will be summarized by treatment group and overall.

### **6.7.3. Adverse Events**

All AEs recorded on the eCRF will be coded using the MedDRA dictionary [version 23.1 or a later version if updated during the study] and classified as treatment-emergent AEs (TEAEs) as follows:

- TEAEs are either events with start date on or after the start of the Treatment Period and up to the end of the study visit, or events with start date prior to the start of the Treatment Period whose severity worsens on or after the start of the Treatment Period.
- Treatment-Emergent Serious AEs (TESAEs) will be defined as TEAEs regarded by the investigator as Serious = “Yes”.
- The relationship between a TEAE and treatment is assessed as related, possibly related, or not related. A treatment-related TEAE will be defined as a TEAE considered by the investigator as related or possibly related to treatment or with unknown / missing relationship to treatment.

- Severe TEAEs are defined as TEAEs assessed as being “Severe” in severity and includes those events where the severity is missing.
- TEAEs leading to discontinuation of treatment are defined as TEAEs where action taken with study treatment is “Permanently Discontinued”.

Adverse events will be summarized by default descriptive summary statistics for categorical variables for the On-Treatment Analysis Set by treatment group and overall as follows:

- An overview of TEAEs including the number and percentage of patients with at least one of each mentioned TEAE type:
  - Any TEAE
    - Leading to discontinuation of study treatment
    - Leading to death
    - mild
    - moderate
    - severe
  - Any study treatment related TEAE
    - Leading to discontinuation of study treatment
    - Leading to death
  - Any serious TEAE
    - Leading to discontinuation of study treatment
    - Leading to death
  - Any serious study treatment related TEAE
    - Leading to discontinuation of study treatment
    - Leading to death
- The number and percentage of patients reporting each TEAE and the count of number of events will be summarized by SOC and PT for the following types of TEAEs:
  - TEAEs Leading to Discontinuation of Study Treatment
  - TEAEs Leading to Death
  - TEAEs by Maximum Severity
  - TEAEs by Relationship to Treatment
  - TEAEs by Relationship and Maximum Severity

- Study Treatment related TEAEs
- Study Treatment Related TEAEs Leading to Discontinuation of Study Treatment
- Study Treatment Related TEAEs Leading to Death
- Serious TEAEs
- Serious TEAEs Leading to Discontinuation of Study Treatment
- Serious TEAEs Leading to Death
- Study Treatment Related Serious TEAEs
- Study Treatment Related Serious TEAEs Leading to Discontinuation of Study Treatment
- Study Treatment Related Serious TEAEs Leading to Death
- The number and percentage of patients who died will be summarized by the primary reason of death
- The number and percentage of patients reporting each TEAE and the number of events will be summarized by PT for TEAEs of clinical endpoint

In the above summaries, patients with more than one TEAE within a particular SOC are counted only once for that SOC. Similarly, patients with more than one TEAE within a particular PT are counted only once for that PT.

For summaries by maximum severity, patients with multiple TEAEs within a particular SOC or PT will be counted under the category of their most severe TEAE within that SOC or PT. TEAEs with missing severity will be included (as Severe) in the overall count of patients with TEAEs, but will not be included in the counts of patients with TEAEs within a SOC or PT.

Summaries by SOCs and PTs will be sorted by SOCs by their Internationally Agreed Order (MedDRA) and PTs within SOC by descending order of total incidence. Where preferred terms tie PTs will be sorted alphabetically.

No formal statistical comparisons of AEs between treatment groups will be performed.

All AE data will be listed and Pre-treatment AEs and TEAEs will be presented together. Treatment-emergence status will be flagged in the listing. The listing will present the relative start and stop day of the AE calculated relative to the first dose of treatment and will be presented for those patients who received at least one dose of treatment. If the AE is “Ongoing” it will be indicated as such in the listing and the relative stop day will not be

calculated. Only original dates will be presented in the listing even though the relative day may be based on an imputed date.

In addition, the following listings will be presented:

- Listing of Deaths
- Listing of Serious TEAEs
- Listing of AEs Leading to Discontinuation of Study Treatment
- Listing of AEs of Clinical Endpoint

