### **10.1 Analysis sets**

- On-Treatment: will consist of all randomized patients who received at least one dose of study drug. Patients will be considered to be on-treatment if within 60 days of their last dose of study drug up to the EoT visit of the randomized treatment period.
- Intent-to-Treat (ITT): all patients randomized and dosed to be analyzed according to randomized treatment assignment. Events occurring from randomization through EoS of the randomized treatment period will be included in the analysis.
- Per Protocol: All randomized patients with a treatment compliance rate of at least 80% and do not have any major protocol violations as defined in the final SAP.
- On-Treatment Extension: will consist of all patients who received at least one dose of abelacimab in the extension period. Patients will be considered to be on-treatment if within 60 days of their last dose of study drug to the EoE visit of the extension period.

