### 3. Analysis Populations and Dates

#### 3.1. Analysis Dates

The analysis dates to be used are defined as:

- EoT date = Earliest of a) the last dose+60 days or b) the EoT visit or c) death date or d) withdraw consent date or e) EoS visit date
- EoS date = Earliest of a) EoS visit or b) death date or c) withdraw consent date or d) lost to follow-up date; if no EoS date available, then impute EoT visit date

In the event that there is an open-label extension period in which the patient enrolls, the following analysis dates to be used are defined as:

- EoT date = Earliest of a) the last dose+60 days or b) the EoT visit or c) death date
- EoS date = Earliest of a) the last dose+60 days or b) the EoT visit or c) death date
- EoE date = Earliest of a) the last dose+60 days or b) the EoE visit or c) death date
- EoS extension date = EoS visit; if no EOS visit date available, then impute EoE date

In accordance with ICH E3 and E9, the following analysis sets will be used for the analyses.

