#### 3.3. On-Treatment Analysis Set

On-Treatment analysis set will consist of all randomized patients who received at least one dose of study drug. Patients will be considered to be on-treatment through the EoT date as outlined in Section 3.1. On-Treatment Analysis Set patients are analyzed according to the actual treatment they received. The On-Treatment Analysis Set will be used for summaries and analysis of demographics and baseline characteristics, treatments and medications, safety endpoints, secondary endpoints, exploratory endpoints and will be the primary analysis set for the analysis of the primary endpoint.

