### 5.1.3. Treatment Period

Data collected on the day of first dose will be assigned to the Treatment Period if the time (HH:MM) of data collection and time (HH:MM) of first dose of treatment are both recorded, and the data collection time is on or after the time of first dose of treatment. Otherwise, the assessment will be assigned to the screening / baseline period. If the time (HH:MM) of data collection is not recorded but the protocol and / or eCRF includes an instruction to the effect that all Day 1 assessments are to be performed prior to the first dose of treatment or randomization, the data collected at Day 1 will be assigned to the screening / baseline period, otherwise it will be assigned to the Treatment Period.

The Treatment Period is defined as the period from the date of the first dose of treatment up to and including the EoT date as defined in Section 3.1.

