### 2.1. Change in the EoT date and EoS date in the randomized phase of the study for patients enrolled in the extension in section 3.1 of the SAP

The analysis dates to be used are defined as:

- EoT date = Earliest of a) the last dose+60 days or b) the EoT visit **-1 day** or c) death date or d) withdraw consent date or e) EoS visit date
- EoS date = Earliest of a) EoS visit or b) death date or c) withdraw consent date or d) lost to follow-up date; if no EoS date available, then impute EoT visit date **-1 day**

**As per the protocol version 5.0, EoT visit and Extension Day 1 will occur on same day.** In the event that there is an open-label extension period in which the patient enrolls, the following analysis dates to be used are defined as:

- EoT date = **Earlier of a) the last dose+60 days or b) the EoT visit -1 day**
- EoS date = **the EoT visit -1 day**
- EoE date = Earliest of a) the last dose+60 days or b) the EoE visit or c) death date
- EoS extension date = EoS visit; if no EOS visit date available, then impute EoE date

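### SAP 6.7.3 does not tie the end of the treatment-emergent AE window to the Section 3.1 dates, so read literally it runs on through the open-label extension

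*SAP*

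**What the plan says.** SAP 6.7.3 defines a treatment-emergent AE (TEAE) by two limbs. For new-onset events: "TEAEs are either events with start date on or after the start of the Treatment Period and up to the end of the study visit". For events already present before treatment, the test is only that the event is one "whose severity worsens on or after the start of the Treatment Period", and no closing date follows. Neither limb refers to the analysis dates in SAP 3.1. The TEAE tables are produced for the On-Treatment Analysis Set by treatment group.

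The dates that bear on this are:

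- **Randomized-phase EoS date, extension patients.** SAP 3.1 (version 2.0) put this no later than the EoT visit. Addendum 2.1 notes that "EoT visit and Extension Day 1 will occur on same day" and moves it to the day before the EoT visit. It sets the EoT date of these patients to "Earlier of a) the last dose+60 days or b) the EoT visit -1 day".
- **EoS visit, extension patients.** SAP 3.1 ties this visit to the end of the extension, and addendum 2.1 keeps the line: "EoS extension date = EoS visit; if no EOS visit date available, then impute EoE date".
- **End of treatment time.** SAP 5.1.3: "The Treatment Period is defined as the period from the date of the first dose of treatment up to and including the EoT date". SAP 3.3: "Patients will be considered to be on-treatment through the EoT date as outlined in Section 3.1". Protocol 10.1 counts patients as on treatment if "within 60 days of their last dose of study drug up to the EoT visit of the randomized treatment period".
- **Separation of periods.** SAP 2.1 sends extension data to a separate analysis plan. Protocol 10.5.1.2 requires separate AE summaries for the On-Treatment and On-Treatment Extension sets.

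None of the seven changes listed in the addendum touches 6.7.3.

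**The concern.** The time-to-event analyses close on analysis dates: SAP 6.6.1 uses the EoT date, and the ITT sensitivity analysis in SAP 6.6.2 uses the EoS date and cites Section 3.1. Section 6.7.3 instead names a visit, and for extension patients that visit comes after all open-label treatment. SAP 3.1 distinguishes the EoS visit from the EoS date, so a programmer has grounds to take the wording at face value.

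The treatment changes at that boundary. Under Protocol 6.4.1, extension patients who had rivaroxaban or abelacimab 90 mg receive 150 mg. Under Protocol 3.3, patients randomized to 150 mg stay on it. Under the literal window, AEs, serious AEs and fatal AEs arising on open-label 150 mg would therefore be tabulated under rivaroxaban or 90 mg for patients who switched. Patients randomized to 150 mg would stay in the right column, but with too long a window.

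**Working it through.** The plan states no figure to reproduce. The check is a comparison of closing dates followed by date arithmetic.

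**1. Where each rule closes for an extension patient**

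- New-onset limb, read literally: the EoS visit, which follows the end-of-extension (EoE) visit.
- Worsening limb: no close.
- Randomized phase under SAP 3.1 version 2.0: no later than the EoT visit.
- Randomized phase under addendum 2.1: EoT visit − 1 day.

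The mismatch was already in version 2.0. The addendum moved the cap by one day.

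**2. Length of the overrun**

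Inputs: Extension Day 1 is the EoT visit (addendum 2.1). The EoE visit is about 30 days after the last injection (Protocol 7.1). The EoS visit is at least 4 weeks, or 28 days, after the EoE visit (Protocol 3.1.4; Protocol 7.1 says about 4 weeks).

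Overrun = (EoE visit + 28) − (EoT visit − 1) = time from EoT visit to EoE visit + 29 days.

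- Assuming one 150 mg dose, on Extension Day 1: 30 + 28 = 58 days past the EoT visit, and 58 + 1 = 59 days past the amended EoS date. Each further monthly dose adds about 30 days.
- The length of the extension cannot be read in the documents. As assumptions: 3 months gives 91 + 29 = 120 days; 6 months, 183 + 29 = 212; 12 months, 365 + 29 = 394; 24 months, 730 + 29 = 759.

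**3. Ceiling on patients who could be put under the wrong treatment**

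Protocol 1.2.2 gives 1,287 randomized 1:1:1. Only the rivaroxaban and 90 mg arms can be misattributed: 1,287 × 2/3 = 858. This assumes equal arms and that every such patient entered the extension. Protocol 4.3 requires ongoing study treatment at the EoT visit, so the true number must be lower. It is a bound, not an estimate.

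**4. Follow-up after the EoT date if both limbs end at the amended EoS date**

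- Extension patient: EoS date = EoT visit − 1 day = EoT date, so 0 days (if the last dose was within 60 days).
- Completer who does not enter the extension: EoT date = EoT visit − 1 day. For abelacimab that is about 30 − 1 = 29 days after the last injection; for rivaroxaban addendum 2.2 makes it the last-dose date itself. The 60-day limit binds in neither case. The EoS visit is at least 28 days after the EoT visit, so follow-up is at least about 28 + 1 = 29 days.
- Permanent discontinuer: the EoS visit is about 30 days after the discontinuation visit (Protocol 6.6), and the EoT date is the earliest of several dates, including last dose + 60 days and the EoS visit. For rivaroxaban the last dose is the discontinuation date. If the visit takes place then, EoS at about day 30 precedes day 60, so the EoT date is the EoS visit and follow-up is 0 days. The same holds for abelacimab when that visit is within about 30 days of the last injection.

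**The case against.** The strongest reply is that this is loose wording, not a conflict. The phrase in 6.7.3 can be read as the EoS analysis date, and on that reading the new-onset limb already stops where it should. Separation of the two periods is specified in SAP 2.1 and Protocol 10.5.1.2, and the extension set is defined in SAP 3.6. The extension SAP and the table shells, which are not among the documents, may set the cut-off explicitly.

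Much of this stands. The reading is available, and the intent to separate is clear. But neither SAP 2.1 nor Protocol 10.5.1.2 puts a cut-off into 6.7.3, and the analysis-date reading does not close the worsening limb. That limb should matter little in practice: Protocol 8.1 counts pre-existing conditions as AEs only if they worsen after study drug starts, so few AE records should carry a pre-treatment start date. Analysis by actual treatment (SAP 3.3) does not help either, because it gives no rule for a patient who takes two treatments in sequence.

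Three stronger readings might be inferred, and the documents do not support them:

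- *The plan pools randomized and extension AEs.* SAP 2.1 and Protocol 10.5.1.2 say the opposite.
- *The addendum created the problem.* Version 2.0 already capped these patients at the EoT visit.
- *6.7.3 contradicts SAP 5.1.3, SAP 3.3 and Protocol 10.1 by running past the EoT date.* Collecting AEs up to a post-treatment visit is a design choice and is compatible with a treatment period that ends earlier.

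**Conclusion.** The point holds as an end point not linked to the analysis dates, with an open worsening limb. Applied literally to extension patients, the rule gives a wrong attribution and not merely a vague one, so it should be corrected. The overrun is at least about 59 days for a switching patient with one extension dose, and longer with more.

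The number of AEs affected cannot be derived, because extension uptake and length are not visible. It is zero if the Section 3.1 dates were programmed or if no patient entered the extension. The consequence is limited to descriptive tables: SAP 6.7.3 plans no formal AE comparisons, and the primary and secondary bleeding analyses close at the EoT date. It should not be read as a threat to the trial's main results.

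**What to change.** Add one line by addendum: both limbs of the TEAE definition end at the randomized-phase EoS date of SAP 3.1 as amended by addendum 2.1, which is the EoT visit − 1 day for extension patients. Assign later events to the On-Treatment Extension set under the extension SAP, if that plan does not already do so. Confirm and record which cut-off was programmed. Optionally, flag or show separately AEs that start after the EoT date. Because the addendum already postdates the database lock of 08Mar2024, label this as a post-lock clarification too.

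The cost is the text and, if the literal window was used, a date filter and a rerun of the AE tables. There are two downsides. An AE on the day of the EoT visit but before the first extension dose goes to the extension. And follow-up after the EoT date differs by extension status: at least about 29 days for completers who stay out, often after a move to standard-of-care anticoagulation, against 0 for extension patients and as little as 0 for permanent discontinuers. The optional flag makes that difference visible.

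### In the two maximum-severity tables, SAP 6.7.3 leaves adverse events with missing severity out of the SOC and PT rows, against its own definition of a severe event

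*SAP*

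**What the plan says.** Two statements in SAP 6.7.3 deal with missing severity.

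- **Definition.** Severe TEAEs are those graded severe, and the category also "includes those events where the severity is missing". No exception is made for any row or table.
- **Counting rule.** The paragraph that begins "For summaries by maximum severity, patients with multiple TEAEs within a particular SOC or PT" says a patient with several events "will be counted under the category of their most severe TEAE within that SOC or PT". It then adds that "TEAEs with missing severity will be included (as Severe) in the overall count of patients with TEAEs, but will not be included in" the patient counts by SOC or PT.

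By its place, the counting rule governs the two SOC/PT summaries that use maximum severity, "TEAEs by Maximum Severity" and "TEAEs by Relationship and Maximum Severity".

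SAP 5.2.2, on missing safety data, refers to 6.7.3 for the handling of missing severity, so these two statements are the whole rule. None of the changes in the post-lock addendum (its sections 2.1 to 2.7) touches 6.7.3.

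**The concern.** The definition is a worst-case convention: an event that nobody graded is treated as severe. The counting rule applies that convention in the overall row and drops it in the SOC and PT rows beneath. In those rows the event is neither treated as severe nor shown as missing; it is simply not there.

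This departs from the SAP's own habits in two other places. In the same section, a missing relationship to treatment counts as treatment-related, with no SOC or PT exception. SAP 6.1 provides a missing category by default for qualitative variables, where appropriate and present.

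What is at stake is the internal consistency of two descriptive safety tables. The same patient can be severe in the overall row and mild, or absent, under the term that was reported. The summary by relationship alone carries no such exclusion, so the same PT can also show different patients in two tables of the same events.

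**Working it through.** The plan gives no figure to reproduce. The check is a comparison of the two statements, followed by a count on assumed data to show direction.

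**Step 1. Apply each statement to one patient in one PT row.** Each case assumes that the patient has no other events under that PT.

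| Events under the PT | PT row under the counting rule | PT row under the definition |
|---|---|---|
| One ungraded | Not counted | Counted, Severe |
| One mild, one ungraded | Counted, Mild | Counted, Severe |
| One graded severe, one ungraded | Counted, Severe | Counted, Severe |

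In all three cases the patient is Severe in the overall row. The PT row agrees with it only in the third. SOC rows behave in the same way.

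**Step 2. General form.** For any SOC or PT row, let G be the patients with at least one graded TEAE in the row, S the patients with at least one TEAE graded severe (a subset of G), and M the patients with at least one ungraded TEAE.

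- Counting rule: total = G; Severe = S.
- Definition: total = G or M; Severe = S or M.
- Shortfall in the total = patients in M but not in G.
- Shortfall in Severe = patients in M but not in S.
- The difference between the two shortfalls is the number of patients shown as mild or moderate who would be Severe under the definition.

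All of these are zero if M is empty.

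**Step 3. Worked example (assumed counts, not from the documents).** Ten patients each have one TEAE, all under the same PT: 4 mild, 3 severe, 3 ungraded. They are taken to be the only patients with a TEAE.

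- Overall row: 4 + 3 + 3 = 10 patients; Severe = 3 + 3 = 6.
- PT row under the counting rule: 4 + 3 = 7 patients; Severe = 3.
- PT row under the definition: 10 patients; Severe = 6, which agrees with the overall row.

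The PT row is 3 short in the total (10 - 7) and 3 short in Severe (6 - 3).

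**Step 4. Reach.** The exclusion is stated only for summaries by maximum severity. None is stated for the overview table, the summary by relationship alone, or the SOC/PT summaries of serious, treatment-related, fatal or discontinuation events. All adverse events are also listed by patient.

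**The case against.** The strongest reply is that the counting rule is a specific display rule that follows a general definition, and that a programmer can apply it without ambiguity. Labelling an ungraded event Severe under a named PT is itself a choice, and leaving it out is another. It can also be said that the case will rarely arise. Protocol 8.1 requires a severity grade for every adverse event, and Protocol 9.1 to 9.3 provide for monitoring, automatic checks and queries. The table shells, which are not available here, may settle the layout.

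The rarity argument stands and keeps the point small. The display argument does not remove the conflict: the definition has no exception, and the counting rule neither cites it nor gives a reason for departing from it.

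A reader might infer more than the documents support, in four ways.

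- **That ungraded events vanish from all SOC and PT tables.** They do not. The exclusion belongs to the two maximum-severity summaries.
- **That a sizeable number of severe cases is hidden.** Assuming that 1% of the 1,287 randomized patients had an ungraded event gives 0.01 x 1,287 = 12.87, about 13. The share has no basis in the documents, and at 0% the result is 0. The adverse event tables use dosed patients rather than all randomized patients. A patient with a graded severe event in the same row is still counted there. At that share, 13 is therefore at most an upper illustration. The events are also ungraded, so any shortfall is against the SAP's own convention and not against known severity.
- **That the loss differs by arm because treatment is open-label.** Nothing in the documents points to this.
- **That SOC and PT rows should add up to the overall row.** They never do, because one patient can appear under several terms. The inconsistency is in how the same event is classified, not in a failed sum.

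**Conclusion.** The conflict is real and limited to the two SOC/PT summaries that use maximum severity. Followed as written, an ungraded TEAE is lost from the total of its SOC and PT rows unless the patient has a graded event in the row. It is lost from the Severe category unless the patient has an event graded severe there. A patient with a mild and an ungraded event under one PT is shown as mild.

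The size depends wholly on how many severities are missing, which the documents do not say and which may be none. The overall row and the overview table are not undercounted. Adverse events are not formally compared between arms, and the primary bleeding analysis does not use these tables. This is a minor correction, worth making because it is cheap and because safety is the purpose of the trial.

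**What to change.** In SAP 6.7.3, replace the exclusion clause with one rule for all levels, for example: *An ungraded TEAE is treated as Severe in the overall, SOC and PT rows; a footnote gives the number of imputed severities by arm.* This follows the existing definition. Showing a missing category at every level would also be consistent, but the definition of a severe TEAE would then have to change too.

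The cost is one sentence and one programming rule applied to two tables. Because the database was locked on 08 March 2024, it also needs a short entry in the post-lock addendum, a route the sponsor has already used. The small downside is that some ungraded events will be labelled Severe under a named term; the footnote lets the reader see how many. If no severity was missing, one sentence saying so closes the point and no table needs to be rerun.
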